Therapeutic interventions are aimed primarily at either 1) up-regulating expression of the frataxin protein (patients all have residual levels of normal protein and experimental approaches have demonstrated proof of principle of this approach with various small drugable molecules), or 2) ameliorating the pathogenic effects of low frataxin levels, namely a) reduced activities of key mitochondrial enzymes involved in energy metabolism that are dependent on Frataxin-dependent mitochondrial iron metabolism (FeS cluster-containing enzymes such as aconitase and OXPHOS enzyme complexes I, II and III, and possibly heme-dependent enzymes such as OXPHOS enzyme complex IV), and b) generalized oxidative stress in mitochondria and its negative consequences on mtDNA, proteins and membrane lipids.

Efficacy of these therapies can be monitored both by scoring clinically-defined neurologic parameters, and also by biochemical measurement of key mitochondrial enzymes, functions or metabolites or by genetic modifiers. Currently, genetic modifier studies have been limited to the lack of DNA samples linked to detailed clinical information that allows for stratification of the disease group based on disease severity and phenotypic variability. Frataxin levels will be a primary biochemical endpoint in therapeutic interventions designed to up regulate the steady-state levels of this protein. Moreover, upregulated frataxin levels will of necessity precede any other markers of clinical efficacy, including neurological scores. Therefore, tests to monitor these levels should be able to use tissue samples that can be obtained repetitively and non-invasively. Examples of such samples are oral epithelial cells obtained by non-invasive gentle cheek swabs and whole blood obtained by standard blood draws or finger prick sampling. Additionally, physiological abnormalities from frataxin deficiency in affected tissues can be monitored using imaging techniques, including ³¹P magnetic resonance spectroscopy (MRS) and MEP.

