3 INVESTIGATIONAL PLAN

3.1 General Schema of Study Design

Pediatric Subjects will be recruited from each site's ongoing practice and the Friedriech Ataxia natural history study and invited to participate in this study. [name] will recruit up to 90 children from his practice to participate at CHOP, and the remaining two sites, UCLA and University of Florida, will recruit up to 20 children in a similar manner to participate. Such subjects will return every 6 months for neurological measures, and biochemical measures (frataxin levels, platelet metabolic biomarkers). At each annual visit a select number of participants at CHOP will also complete tests assessing anatomical biomarkers. Data will be analyzed based on the change in measures over time to identify those that change serially in FA and the ability of disease features to predict such change.

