Aim 2: Results will be summarized with standard descriptive statistics using parametric or non-parametric methods, as appropriate given the variable distributions. In this biochemical aim, the major analysis will examine the relationship of frataxin levels and downstream biomarkers with disease progression. This will be performed in 2 ways. First using cross sectional data, we will construct mixed linear models that allow the assessment of their relationship of marker values (frataxin, 13C metabolite levels, Apo A1) to age, GAA repeat length and sex. Secondly, we will assess the change in values over time both in absolute value and percent change to understand the overall meaning of results. In addition, the change over time will be examined in relation to age, sex, and GAA repeat length in linear models. We will also examine the levels of each marker at baseline with the change in clinical measures from aim 1. This will allow us to understand the degree to which clinical change reflects individual biochemical events and whether clinical and biochemical events correlate temporally. This analysis will be supplemented by analysis assessing whether the change in levels of the biomarkers predicts clinical change.

Aim 3. Each of the measures here (MEP, CrCEST) has differentiated FRDA subjects from controls in previous studies. For this proposal though, the crucial analyses should ascertain the relationship between physiological values from CrCEST and MEP and disease status from clinical measures. Results will be summarized with standard descriptive statistics using parametric or non-parametric methods, as appropriate given the variable distributions. In cross sectional analyses, results from each of the outcome measures (frataxin levels, platelet metabolic markers, ApoA-1, and recovery time from CrCEST) will

be used as dependent variables in multiple linear regression models or mixed models examining the independent effects of age, GAA repeat length and sex as dependent variables. This will allow us to define the degree to which each outcome marker is predicted by genetic severity (GAA repeat length), disease progression (age) or both. We will also directly correlate results between MEP and CrCEST to ascertain the degree to which they reflect the same construct (FRDA disease progression). Finally, we will examine correlations and regression modelling between physiological results and clinical measures (Aim 1) and frataxin levels (Aim 2)

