4.9 Sample Size and Power

The sample size of main parts of the study is dictated by previous studies and by practicality. Previous power calculations suggest that even using even well-defined clinical measures, the sample size for therapeutic trials will be more than 100 subjects, even using selected cohorts (9-13). However, the tests performed in the present study generally show robust differences between FRDA subjects and controls, and should provide more sensitive measures of disease if they retain sufficient fidelity in children. A sample size of 110 subjects should allow us to assess the independent effects of age, sex and genetic severity (GAA length) on measure results, facilitating a true understanding of the degree they can be used in children. One hundred subjects is also practically the upper limit of intervention studies in rare disease, and thus is appropriate for this study. In the present, study subjects will return every year for MEP and CrCEST, and every six months for clinical testing and blood tests through 36 months. MEP and CrCEST will have smaller samples size (30 and 12 respectively) as they are more precise but more labor intensive tests. Total duration for each subject is approximately 3-4 years, and initial recruitment will occur over a 2 year period. In the present study the goal is to define how each of the tests change over time in children with FRDA, and the factors (age, GAA length) that predict such changes. Each marker has been differentiated from control values previously; however, here control subjects will be used only if needed to confirm the differences, to provide a context and to be sure that tests perform similarly in all sites as a quality control measure.

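### Aim 2 draws a conclusion about timing from baseline marker levels, and sets no interval or lag for asking whether marker change predicts clinical change

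*Combined protocol and SAP*

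**What the plan says.** Section 4.8, Aim 2, first models marker values against age, GAA repeat length and sex, then marker change against the same three factors. Two further analyses link markers to clinical outcome.

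- Baseline level: "We will also examine the levels of each marker at baseline with the change in clinical measures from aim 1". The next sentence says this will give an understanding of how far clinical change reflects biochemical events, and of "whether clinical and biochemical events correlate temporally".
- Change: a supplementary analysis will assess "whether the change in levels of the biomarkers predicts clinical change".

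Neither has a time window, a lag, a model or covariates.

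The data for a time-ordered analysis are planned. Section 3.1 has neurological and biochemical measures every 6 months, and section 4.9 has subjects returning "every six months for clinical testing and blood tests through 36 months". The visit list in 3.1.2 has months 0, 6, 12, 18, 24 and 36 plus a subject-dependent Visit 7, with no 30-month visit. Section 4.1 says that remote visits yield no samples.

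**The concern.** A baseline level precedes later clinical change, so it can be tested as a prognostic factor. It does not vary within a child, so it cannot show whether biochemical and clinical changes move together or which comes first.

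The change analysis could address timing, but nothing in the plan orders the two changes. If both run over the same follow-up, three explanations fit equally well: the marker moves first, clinical status moves first, or some children simply progress faster on everything. A report that marker change predicts progression would then rest on an association that cannot tell these apart. This matters because section 4.8 makes the relation of frataxin and downstream markers to disease progression the major analysis of Aim 2, and section 2.2 wants markers suitable for repeated monitoring of therapy.

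**Working it through.** The plan gives no effect size, correlation, lag or power for these analyses, so there is no figure to reproduce. Two checks apply.

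**1. Can the planned comparisons show order?**

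Input from section 4.9: n = 110. Everything else is assumed. Work in 6-month increments. Marker increment M(t) and clinical increment C(t) each start as independent noise, u(t) and e(t), with variance 1. Baseline marker level is the sum of four increments before entry. Four scenarios, 1000 runs each:

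- Marker first: C(t) = e(t) + 0.6·u(t−1)
- Clinical first: M(t) = u(t) + 0.6·e(t−1)
- Same interval: C(t) = e(t) + 0.6·u(t)
- Shared speed, no link: M(t) = u(t) + s and C(t) = e(t) + s, where s is one value per child with variance 0.25

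Mean simulated correlations:

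| Scenario | Baseline level vs 0–36 month clinical change | 0–36 month change vs 0–36 month change | 6-month marker change vs next clinical change | 6-month clinical change vs next marker change |
|---|---|---|---|---|
| Marker first | 0.11 | 0.42 | 0.51 | 0.00 |
| Clinical first | 0.00 | 0.43 | 0.00 | 0.51 |
| Same interval | 0.00 | 0.51 | 0.00 | 0.00 |
| Shared speed only | 0.55 | 0.60 | 0.20 | 0.20 |

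The main entries can be checked by hand:

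- Baseline, marker first: 0.6/√(4 × 6 × 1.36) = 0.6/√32.64 = 0.105.
- Baseline, shared speed: covariance 4 × 6 × 0.25 = 6; variances 4 + 16 × 0.25 = 8 and 6 + 36 × 0.25 = 15; 6/√120 = 0.548.
- Same-period, marker first: 5 × 0.6/√(6 × 6 × 1.36) = 3/√48.96 = 0.429. Clinical first is identical by symmetry.
- Same-period, shared speed: 9/15 = 0.60.
- Lagged, marker first: 0.6/√1.36 = 0.514. Lagged, shared speed: 0.25/1.25 = 0.20.

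Three readings follow.

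- The baseline analysis was significant (two-sided 0.05) in about 20% of runs when the marker truly led, and in 100% when there was no link beyond shared speed. It picks up prognosis, not timing.
- The same-period correlation was significant in over 99% of runs in all four scenarios, so it cannot separate them.
- Lagging separates marker-first from clinical-first, but lagging alone is not enough. Under shared speed both lagged correlations were 0.20 and significant in about 94–95% of runs. Wider windows (0–12 against 12–24 months) gave 0.33 in both directions, again significant in about 94–95%. Using within-child-centred interval changes with visit effects, in both directions, brought false positives down to 6–8% and picked out the true direction when there was one.

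**2. How many lagged pairs does the schedule give?**

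- Visits at 0, 6, 12, 18, 24 and 36 months give 5 intervals of 6, 6, 6, 6 and 12 months.
- They form 4 consecutive pairs, of which 3 have both intervals 6 months long: 3 × 110 = 330 with no loss (4 × 110 = 440 if the unequal pair is used).
- If there is a 30-month visit, as sections 3.1 and 4.9 imply, there are 6 equal intervals and 5 pairs: 5 × 110 = 550.
- One remote visit is costly. With no sample at month 12, marker change is lost for 6–12 and 12–18 months, leaving 1 of the 3 equal pairs in each direction. For the 9-hole peg test, which remote visits also omit, none of the 3 remains.

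**The case against.** Several objections have force.

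- A reader might infer that the plan claims marker change predicts clinical change. It does not: it will assess whether this is so.
- A reader might infer that the plan compares changes over the same period. It does not say that. The interval is unstated, so the defect is an unspecified analysis and not a stated wrong one.
- A reader might take section 1.1 to make biochemistry-first a hypothesis of this study, because it says "upregulated frataxin levels will of necessity precede any other markers of clinical efficacy, including neurological scores". That sentence concerns frataxin raised by treatment, and it is used there to argue for samples that can be taken repeatedly. This study gives no treatment, and section 2.2 lists no aim about temporal precedence. The sentence shows why readers would care about order, and no more.
- Relating baseline level to later change is legitimate as a test of prognosis.
- The phrase about temporal correlation may be meant loosely, as association over time, and both analyses are presented as additions.

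The last point does not remove the problem. Even on a loose reading, association over time needs marker values that vary over time. Before the supplementary analysis, Aim 2 relates marker change only to age, sex and GAA length. The supplementary analysis is the only one that sets marker change against clinical change, and it is the one without an interval.

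**Conclusion.** The point holds in this form: as written, the baseline-level analysis cannot support the conclusion on timing attached to it, and the change analysis has no interval or lag that would let it speak to prediction. If the changes are taken over the same follow-up, the result is concurrent association. In the illustration, marker-first and clinical-first were indistinguishable (0.42 and 0.43), and shared speed alone gave a larger value (0.60).

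That first statement needs no assumption beyond one baseline value per child. The correlations rest on assumed effect sizes and show the principle, not what this study will find. The count of 330 equal-interval pairs assumes full enrolment, no missed samples and the visit list in 3.1.2.

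The rates of change that section 4.7 names as primary endpoints are not affected. The point should be settled before the Aim 2 analysis is run.

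**What to change.** In section 4.8, Aim 2:

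1. Describe the baseline-level analysis as prognostic only: marker level against later clinical change, adjusted for age, sex and GAA repeat length. Remove the conclusion about timing from it.
2. For temporal association, specify a longitudinal model of interval changes on the paired visits. Relate marker change in one interval to clinical change in the next, and fit the reverse as well. Include visit or time terms. Separate within-child from between-child effects, so that a child's overall rate of progression is removed, with age, sex and GAA length as covariates for the between-child part. State how the 12-month interval and missed samples are handled.
3. Label any same-period correlation of changes as concurrent association, not prediction.

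Judge order from the sign and size of both directions together, not from a single p-value. With so few intervals per child, centring can itself push an estimate somewhat away from zero, so the chosen model should be tried on simulated data with the real visit schedule first.

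The 30-month visit implied by sections 3.1 and 4.9 but absent from 3.1.2 must be reconciled, because it decides which equal lags exist.

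The cost is analysis work only. The downside is wider intervals for the lagged estimates: of at most 330 pairs, removing 110 child means leaves 330 − 110 = 220 within-child contrasts, before any loss. If the sponsor prefers not to do this, limiting the Aim 2 wording to association is enough.

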3.4 Study Population

3.4.1 Inclusion Criteria

1) Males or females age 2 to 18 years.

- Genetically confirmed diagnosis of FRDA or clinically confirmed diagnosis of FRDA, pending confirmatory genetic testing through a commercial or research laboratory
- 3) Parental/guardian permission (informed consent) and if appropriate, child assent.
- 4) Weight \geq 10 kg (for the MEP measures only)

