4.6 Abstracted Data Elements

Friedreich Ataxia Clinical Outcome Measures Study (CHOP IRB# 01-002609): Below are the listed data elements that will be abstracted from this study. This includes data collected before and during the participant's enrollment.

- Functional Staging for Ataxia Score
- Friedreich Ataxia Rating Scale (FARS)
- Medical History Update- FA Symptoms Review
- Medical History Update Medical Conditions Log
- Medical History Update Medications
- Vital Signs- height, weight, BMI, blood pressure
- 9 Hole Peg Test
- Timed 25 Foot Walk
- Extended Timed Walks
- Activities of Daily Living
- Pediatric Quality of Life Questionnaires

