4.7 Primary and Secondary Endpoints

The primary goal of this study is to gather long-term serial quantitative clinical data using the measures validated during the three years of the study.

Aims 1: The primary endpoint (s) are the change in each of the clinical measures over time. The rate of change of each of these will be compared for responsiveness to change (SD of change/mean change).

Aim 2: Biochemical measures: The rate of change of frataxin and each platelet biomarker will be determined as primary endpoints. The rate of change over time will be determined to define which measures are most sensitive to disease progression.

Aim 3: Anatomical measures: The primary endpoints are the post exercise recovery time, Tau, for CrCest and the MEP size for MEP testing. The rate of change over time will be determined to define which measures are most sensitive to disease progression.

The secondary analyses are:

The rate of change of each measure the (neurological measures, biochemical measures and anatomic measures) as a function of age, GAA repeat length and sex, as determined by linear regression models

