4.8 Statistical Methods

Aim 1: Results will be summarized with standard descriptive statistics using parametric or non-parametric methods, as appropriate given the variable distributions. Each of the parameters tested here have been abnormal in FRDA patients previously, including children. However, the specific features of how they behave in large pediatric cohorts is unclear. Thus, the most important analyses will be how the tests behave over time and how they reflect disease severity. Data for test-retest for the first 5 subjects at the primary site will be evaluated by determining the coefficient of variation over the tests. This will be performed immediately after study initiation as a separate analysis to confirm that the initial protocols have sufficient reproducibility to be useful. Full data collection will then proceed. Data from measures that were repeated (timed walks, TUG, CCFS tests) will be analyzed as means of the repeated tests and test retest features between trials. CCFS values will be analyzed as each hand separately (dominant vs non dominant) and hands together. Each test will be assessed in regression or mixed linear models accounting for age, sex and GAA repeat length. In addition the change over time will be established as well as the reproducibility of that change.

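### Section 4.8 reads age as disease progression in children aged 2 to 18, where age also carries maturation; raw change in the walks, T25FW and TUG likewise mixes growth with disease

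*Combined protocol and SAP*

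**What the plan says.** Section 4.8 (Aim 3) plans cross-sectional regression or mixed models "examining the independent effects of age, GAA repeat length and sex". It then says how they will be read: they show the degree to which each marker is "predicted by genetic severity (GAA repeat length), disease progression (age) or both". The outcomes listed for that analysis are frataxin, platelet metabolic markers, ApoA-1 and CrCEST recovery time. Section 3.4.1 admits "Males or females age 2 to 18 years".

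The same three covariates recur throughout. For Aim 1, "Each test will be assessed in regression or mixed linear models accounting for age, sex and GAA repeat length". For Aim 2, "the change over time will be examined in relation to age, sex, and GAA repeat length in linear models". The secondary analyses in section 4.7 also use age, GAA length and sex. No section puts height, age norms, age at onset or disease duration into a model.

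For Aim 1, section 4.7 states: "The primary endpoint (s) are the change in each of the clinical measures over time". Measures are then compared by SD of change divided by mean change.

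On data, section 4.6 lists "Vital Signs- height, weight, BMI, blood pressure" among the items taken from the linked natural history study (FACOMS). Section 3.1.5 limits this to children enrolled in both studies whose consent covers future use. Section 4.1 includes a medical history, but names neither age at onset as a data item nor height as a procedure.

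On controls, section 3.2 says not applicable. Section 4.9 says "here control subjects will be used only if needed to confirm the differences", and adds context and a check that tests perform alike across sites.

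**The concern.** There are two separate problems.

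**The age label.** Between ages 2 and 18, a difference in age is a difference in maturation as well as in possible time with disease. Two children of the same age can also be at very different times from onset. A marker that shifts with normal development would be reported as predicted by disease progression. A marker with a real disease trend in the opposite direction to development could look flat.

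**Raw change in Aim 1.** A growing child tends to walk further and faster for reasons unrelated to FRDA. For tests that depend on body size, three-year change is the sum of growth and disease. Aim 1 is directed at the youngest children, and section 1.1 names poor sensitivity of measures in children as the gap to be filled. A responsiveness ranking built on net change could therefore place a test that detects disease below one that does not. This is because of growth in the mean, not because the test fails.

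**Working it through.** The plan gives no figure on this point to reproduce. Section 4.9 states no effect size, SD, alpha or power. The calculations below are illustrations, and every input not attributed to the plan is an assumption.

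**1. Growth in walking distance over three years.** The plan supplies the 36-month follow-up. Assumed: starting height h, growth g cm per year, distance proportional to height to the power p. Relative gain = ((h + 3g)/h)^p − 1.

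| h (cm) | g (cm/year) | (h + 3g)/h | p = 0.5 | p = 1 |
|---|---|---|---|---|
| 110 | 6.5 | 129.5/110 = 1.177 | 8.5% | 17.7% |
| 130 | 5.5 | 146.5/130 = 1.127 | 6.2% | 12.7% |
| 150 | 5 | 165/150 = 1.100 | 4.9% | 10.0% |

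The range is about 5% to 18%. At g = 0 the gain is zero, so for adolescents near the end of growth it falls below 5% toward nothing. Eligible children shorter than 110 cm are outside the range shown.

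**2. What the age coefficient estimates.** Assumed, in residual-SD units with positive meaning worse: age uniform on 2 to 18; onset uniform between 30% and 100% of current age; disease effect d = 0.10 per year of duration; maturation effect m per year of age; GAA length independent of onset. Duration is then on average 0.35 of age, because the fraction runs evenly from 0 to 0.70. With only age, GAA length and sex in the model:

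age coefficient = m + 0.35 × 0.10 = m + 0.035

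| m | Age coefficient, planned covariates | Duration coefficient, if added |
|---|---|---|
| −0.20 | −0.165 | 0.10 |
| −0.10 | −0.065 | 0.10 |
| −0.035 | 0 | 0.10 |
| 0 | +0.035 | 0.10 |
| +0.10 | +0.135 | 0.10 |

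A simulation with 4,000 data sets of n = 110 per setting agrees to within 0.001. The true disease effect is the same in every row, yet the age coefficient changes sign. Even with no maturation (m = 0) it is only about a third of the effect per year of duration.

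**3. Precision.** At n = 110 the sampling SD of the duration coefficient is 0.044 to 0.045, against 0.021 to 0.022 for the age coefficient in the planned model. At n = 12 (run at m = −0.10) it is 0.19, nearly twice the effect of 0.10. Scaling by root n gives 0.044 × √(110/30) = 0.084 at n = 30, almost as large as the effect.

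**4. Within-child change.** Over three years age and duration both rise by three, so mean change = 3 × (0.10 + m). With an assumed SD of change of 1:

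| m | Mean change | SD/mean |
|---|---|---|
| +0.10 | 0.60 | 1.7 |
| 0 | 0.30 | 3.3 |
| −0.05 | 0.15 | 6.7 |
| −0.10 | 0 | undefined |

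Because the two clocks run together within a child, a duration term cannot split this change. It separates growth from disease only through differences in onset between children.

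**The case against.** The strongest reply is about scope. Age is called progression once, for the Aim 3 cross-sectional list. The walks, TUG, BBS and peg tests are not on that list, and for Aim 1 the plan only adjusts for age. A reader might infer that the plan labels age as progression for every measure; it does not. This stands, and it is why the label and the raw-change endpoint are treated here as two issues.

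Second, a reader might infer that growth will cancel decline and that responsive tests will be discarded. The documents do not support that. They give no growth effect for any measure and contain no rule for dropping one. A measure unaffected by growth has no growth bias. Section 4.9 sets the goal as describing how tests change in children with FRDA, for which net change is a legitimate target. Section 5.6 also excuses non-ambulatory, more severely affected and cardiomyopathy subjects from the timed walks.

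Third, the plan has partial safeguards. Aim 3 calls its crucial analyses those that relate CrCEST and MEP to clinical disease status, so age is not the only reference. Section 4.7 models rate of change against age, which would reveal different slopes in younger children. These help, but those clinical measures are not themselves adjusted for growth, and a slope that varies with age does not say why.

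Fourth, the data for a remedy are incomplete. FACOMS height reaches only consenting dual enrollees. Section 3.4.1 does not require symptoms, so time since first symptom may be undefined for some children. This stands and limits the fix.

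**Conclusion.** The point holds in two limited parts. For frataxin, platelet markers, ApoA-1 and CrCEST recovery time, the stated reading of the age coefficient as disease progression is not justified in children aged 2 to 18 with no duration or growth term. This needs no numerical assumption beyond age carrying both processes. For the timed walks, T25FW and TUG, raw within-child change includes growth. Its size and direction cannot be derived from the documents; the 5% to 18% depends wholly on the assumed heights, growth rates and exponent. It concerns walking distance, not the markers to which the age label applies.

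A reader might also infer that adding disease duration would repair the primary endpoint. It would not, for the reason in step 4 of the working. This is an inexpensive improvement to interpretation and reporting, not a flaw that invalidates the study.

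**What to change.** In section 4.8:

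1. Replace the description of age as disease progression with *age (growth and disease combined)*.
2. For measures taken in all 110 children, keep the model with age, GAA length and sex. Add a supplementary between-child model with time since first symptom, where onset is available from the medical history. State how many children have no onset date, and that this model does not separate growth from disease in within-child change.
3. For the timed walks, T25FW and TUG, report a height-adjusted or height-scaled change beside the raw change where height is available, from FACOMS vital signs or recorded at study visits. State that net change in BBS, peg and click tests also includes maturation, since height scaling is not proposed for them.
4. Add no terms for CrCEST (n=12) or MEP (n=30), where they could not be estimated usefully.

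The cost is plan wording, extraction of onset from the medical history, and height recording for children not in FACOMS. Some precision is lost because age is correlated with duration and with height. As the raw analyses are kept, nothing already planned is given up.
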